¹ Stryker Neurovascular Excelsior® XT-27® (0.027" ID, 2.9F/2.7F OD, 150cm Length)

² Detachable Coil Power Supply: Stryker Neurovascular InZone® Detachment System, REF M00345100940

³ Power Supply Detachment Cable: Stryker Neurovascular IZDS Connecting Cable, REF 00345110250

| Cerus Endovascular | Document Number DNX099-01 | Rev F | Page 10 of 106 |
|----------------------------|---|---------------|----------------|
| Investigational Protocol | Title | | |
| Confidential & Proprietary | Contour Neurovascular System [™] European Pre-M Study (CERUS) | 1arket Unrupt | ured Aneurysm |

| Cerus Endovascular | Document Number DNX099-01 | Rev F | Page 11 of 106 |
|----------------------------|---|----------|----------------|
| Investigational Protocol | Title | | |
| Confidential & Proprietary | Contour Neurovascular System [™] European Pre-Market Unruptured Aneurysm Study (CERUS) | | |

| Objective and Endpoints | The primary objective of this study is to document the safety and performance of the Contour Neurovascular System. The data from the study will be reported as a Pre-Market study to the Notified Body to support CE Mark approval. In addition, the data may be used to support US approval by the Food and Drug Administration (FDA) to market the Contour device in the United States. |
|-------------------------------|---|
| | 1. Primary Safety Endpoint: |
| | The proportion of subjects with death of any non-accidental cause or any major disabling stroke within the first 30 days after treatment or major disabling stroke or death due to neurological cause from day 31 to 6 months after treatment. |
| | Note: Major Disabling Stroke is defined as an episode of neurological signs or symptoms that persist beyond 24 hours accompanied with evidence of ischemia/infarction on imaging that results in an increase of NIHSS from baseline by ³ 4 points and/or an increase from mRS baseline by >2. |
| | 2. Primary Performance Endpoint: |
| | To demonstrate the occlusion rate on the 6 month angiogram as adjudicated by a core laboratory. Success will be defined as complete occlusion demonstrated by a Grade 1 using the Raymond Roy Scale. |

| Cerus Endovascular | Document Number DNX099-01 | Rev F | Page 12 of 106 |
|----------------------------|---|----------|----------------|
| Investigational Protocol | Title | | |
| Confidential & Proprietary | Contour Neurovascular System TM European Pre-Market Unruptured Aneurysm Study (CERUS) | | |

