6.1 Potential Risks

The potential risks and complications of the device will be explained to the patients receiving the implanted device. The risks similar to the risks of other devices approved for endovascular aneurysm treatment are well known.

| Cerus Endovascular | Document Number DNX099-01 | Rev F | Page 26 of 106 |
|----------------------------|--|----------|----------------|
| Investigational Protocol | Title | | |
| Confidential & Proprietary | Contour Neurovascular System TM European Pre-Market Unruptured Aneurys Study (CERUS) | | ured Aneurysm |

These risks may cause significant neurologic complications such as a cerebrovascular accident (CVA) and possibly death, and include but are not limited to the following: infection, abnormal bleeding or clotting, pain, injury to the groin site, injury to the aneurysm including bleeding and/or rupture, decreased blood flow to the brain or other parts of the body, inability of the device to totally prevent blood from flowing inside it, movement of the device within the aneurysms or to another location in the body.

| Anticipated Risk by Clinical Category | Percent Anticipated Risk Occurence | Specific Anticipated Risks |
|---|--|----------------------------|
| Neurovascular Sequelae | Rarely (< 5%) | CVA – ischemic |
| * | Rarely (< 5%) | CVA – hemorrhagic |
| | Rarely (< 5%) | Aneurysm rupture |

| Anticipated Risk by Clinical Category | Percent Anticipated Risk Occurence | Specific Anticipated Risks |
|---|--|---|
| | Rarely (< 5%) | Blood vessel dissection |
| | Rarely (< 5%) | Blood vessel perforation/rupture |
| | Rarely (< 5%) | Subarachnoid hemorrhage |
| | Rarely (< 5%) | Parenchymatous hematoma |
| | Rarely (< 5%) | Intraventricular hemorrhage |
| | Rarely (< 5%) | Thrombosis with resultant occlusion of aneurysm parent artery of other blood vessel |
| | Rarely (< 5%) | Embolism with resultant occlusion of blood vessel |

| Cerus Endovascular | Document Number DNX099-01 | Rev F | Page 27 of 106 |
|----------------------------|--|---------------|----------------|
| Investigational Protocol | Title | | |
| Confidential & Proprietary | Contour Neurovascular System TM European Pre-M Study (CERUS) | larket Unrupt | ured Aneurysm |

| | Less Likely (5-15%) | Device migration – from the aneurysm to a distal site |
|---|--|---|
| | Likely (>15%) | Headache |
| | Rarely (< 5%) | Cranial nerve palsy |
| | Rarely (< 5%) | Intra-cranial hypertension |

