7.9 Follow-Up

Following discharge, the subject will have a follow-up visit at 1 month, 6 months and 12 months after the implant procedure. At each study visit, the subject shall be assessed for any new adverse events (AEs). A standard neurologic examination should be performed to evaluate for any new adverse events. A modified Rankin Scale (mRS) will be recorded at each follow-up visit. It is expected that most target IAs will be asymptomatic and the likelihood of post-placement neurologic changes is very low. The NIH Stroke Scale

| Cerus Endovascular | Document Number DNX099-01 | Rev F | Page 35 of 106 | | | | |
|----------------------------|--|---------------|----------------|--|--|--|--|
| Investigational Protocol | Title | | | | | | |
| Confidential & Proprietary | Contour Neurovascular System TM European Pre-M Study (CERUS) | larket Unrupt | ured Aneurysm | | | | |

assessment should be obtained within 24 hour after a stroke in the event a subject is diagnosed with a stroke. Cerebral angiography will be repeated at 6 months. The cerebral angiography will include a 3D angiogram. The investigator should ensure that follow-up angiography is done with identical views to maximize the ability to compare baseline and post-treatment views. All angiographic images should be submitted to the independent core laboratory. The target IA status shall be evaluated by an independent core laboratory.

The study's schedule of assessments and post-treatment visit windows are shown in Table 4.

| | Baseline [#] | Procedure | Discharge |) 1-month 1 weeks | months 1 month | 12 months 1 month |
|--|-----------------------|-----------|-----------|-------------------------|-------------------|----------------------|
| Medical history and medications | Х | | | | | X |
| Neurologic Exam | Х | | Х | Х | X | X |
| NIH Stroke Scale | Х | X^* | X^* | X^* | X^* | Х |
| Modified Rankin Scale (mRS) | Х | | X** | X** | X** | X |
| Pregnancy test (pre-menopausal female) | X | | | | | |
| CT angiography (CTA) ^ | X# | | | | | |
| Magnetic Resonance Angiogram (MRA) ^ | X [#] | | | | | |
| Cerebral Angiogram (DSA) ^ | X# | X | | | X | |
| | w/3D | w/3D | | | w/3D | |
| Adverse Event assessment | | Х | Х | Х | X | X |
| Procedure Information | | Х | | | | |
| Aneurysm Occlusion Status – | | | | | | |
| Raymond Roy and general assessment on study form ^{##} | | Х | | | X | |

Table 4. Schedule of Assessments

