10.5 Endpoints

10.5.1 Primary Endpoints

Primary Safety Endpoint:

| Cerus Endovascular | Document Number DNX099-01 | Rev F | Page 43 of 106 | | |
|----------------------------|---|----------|----------------|--|--|
| Investigational Protocol | Title | | | | |
| Confidential & Proprietary | Contour Neurovascular System TM European Pre-Market Unruptured Aneurysm Study (CERUS) | | | | |

The proportion of subjects with death of any non-accidental cause or any major disabling stroke within the first 30 days after treatment or major disabling stroke or death due to neurological cause from day 31 to 6 months after treatment.

Note: Major Disabling Stroke is defined as an episode of neurological signs or symptoms that persist beyond 24 hours accompanied with evidence of ischemia/infarction on imaging that results in an increase of NIHSS from baseline by ³ 4 points and/or an increase from mRS baseline by >2.

Primary Performance Endpoint:

To demonstrate the occlusion rate on the 6 month angiogram as adjudicated by a core laboratory. Success will be defined as complete occlusion demonstrated by a Grade 1 using the Raymond Roy Scale.

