10.7 Sample Size Rationale

This is a single arm study designed to provide adequate data for the purpose of CE Mark. It is expected the 30 patients with evaluable data at 6 month follow-up will show adequate evidence of safety and performance for the application for CE Mark of the device. No formal hypothesis testing of the study endpoints will be performed, therefore no formal sample size was calculated.

11 Additional Trial Characteristics

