19.3 European Pilot Clinical Study – Contour

A synopsis for the EU Pilot study is included below. The study includes 3 sites in the United Kingdom and one site in Hungary.

| Study Title | Pilot Study of the Contour Neurovascular System TM |
|---------------------|--|
| Device Name | Contour Neurovascular System TM |
| Primary Objective | To collect and report the safety variables data of the Contour Neurovascular System TM |
| Secondary Objective | To collect and report the efficacy variables data of the Contour Neurovascular System [™] |

| Cerus Endovascular | Document Number DNX099-01 | Rev F | Page 82 of 106 |
|----------------------------|--|---------------|----------------|
| Investigational Protocol | Title | | |
| Confidential & Proprietary | Contour Neurovascular System TM European Pre-M Study (CERUS) | 1arket Unrupt | ured Aneurysm |

| Design | Prospective, single arm, multi-centre study |
|------------------------------|---|
| Assigned Intervention | Endovascular treatment with the Contour Neurovascular System TM for an unruptured intracranial aneurysm (IA) |
| Target Patient Population | Patients with unruptured IAs suitable for treatment with the Contour Neurovascular System TM and who meet study eligibility criteria |
| Primary Variables | Safety: Safety variables are the occurrence and frequency of adverse events (AE)s, adverse device effects (ADE)s, serious adverse events (SAE)s, serious adverse device effects (SADE)s and unanticipated serious adverse device effects (USADE)s |
| | Specific AEs associated with this procedure that shall be evaluated include but are not limited to: blood vessel perforation or rupture, unintended thrombosis, adverse tissue reaction, infection, and hematoma formation, and major ipsilateral stroke/subarachnoid hemorrhage (SAH) or death due to neurologic cause within six (6) months after treatment |
| Secondary Variables | Efficacy: Efficacy variables are related to the ability of the device to embolize the aneurysm and shall be analyzed relative to the baseline visit. The variables to be collected and reported shall include but are not limited to: |
| | Angiographic and/or magnetic resonance imaging (MRI)/MR angiogram (MRA) assessment of aneurysm occlusion including evaluation of occlusion grade, parent vessel patency, physical positioning, occlusion durability, and any device migration |
| Sample Size | A maximum of forty-five (45) subjects |
| Number of Sites | A maximum of five (5) clinical study sites |

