Study Purpose:	Cerus Endovascular is sponsoring a prospective, multi-center trial to document the safety and performance of the Contour Neurovascular System [™] ("Contour"). The purpose of the study is to document safety and performance of the Contour in treatment for patients with intracranial aneurysms (IA). The data from the study will be reported as a Pre-Market study to the Notified Body to support CE Mark approval.
Study Design:	The study is a prospective, single arm, multi-center study.
Objective and Endpoints:	The primary objective of this study is to document the safety and performance of the Contour Neurovascular System. The data from the study will be reported as a Pre-Market study to the Notified Body to support CE Mark approval. In addition, the data may be used to support US approval by the Food and Drug Administration (FDA) to market the Contour device in the United States. 1. Primary Safety Endpoint: The proportion of subjects with death of any non-accidental cause or any major disabling stroke within the first 30 days after treatment or major disabling stroke or death due to neurological cause from day 31 to 6 months after treatment. Note: Major Disabling Stroke is defined as an episode of neurological signs or symptoms that persist beyond 24 hours accompanied with evidence of ischemia/infarction on imaging that results in an increase of NIHSS from baseline by ³ 4 points and/or an increase from mRS baseline by >2. 2. Primary Performance Endpoint: To demonstrate the occlusion rate on the 6 month angiogram as adjudicated by a core laboratory. Success will be defined as complete occlusion demonstrated by a

Cerus Endovascular	Document Number DNX099-13	Rev A	Page 5 of 9
Statistical Analysis Plan	Title Statistical Analysis Plan for: Contour Neurovascu	lar System TM	European
Confidential & Proprietary	PreMarket Unruptured Aneurysm Study (CERUS))	Duropeun

Secondary Measures	Additional measures will be summarized:	
	 Secondary Safety: Serious Adverse Events (SAE) associated with the procedure or device All serious neurological adverse events 	

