Two patient populations will be considered in the analyses, an Intent-to-Treat (ITT) population and a Per Protocol population (PP). The ITT population includes all patients. The PP population will include subjects who complete 6 months of follow-up, die prior to their 6-month clinic visit, or are study failure (withdrawal from study to obtain alternate treatment). The PP will exclude patients with any major protocol violation that affects proper study inclusion or significant outcomes. Endpoints will be evaluated in the PP and ITT populations.

Any patient for whom a failed implant attempt is performed will be followed for 1 month, or until resolution of any potential device or implanted related adverse events, whichever occurs last.

Any patient who is consented but has no implant attempt will be study exited.

6 General Statistical Principles

The analysis for all primary and secondary study endpoints and baseline, procedural and follow-up characteristics will be performed on an intent-to-treat analysis population which will include all available data for all enrolled subjects. Standard summary statistics will be calculated for all study variables. For continuous variables, statistics will include means, standard deviations, medians and ranges. Categorical variables will be summarized in frequency distributions. Missing data will not be imputed. The number of data values available for each analysis will be reported so that the impact of missing data can be seen.

Statistical analyses will be conducted in SAS version 9.4 or above (SAS Institute, Cary, N.C.).

Cerus Endovascular	Document Number DNX099-13	Rev A	Page 7 of 9	
Statistical Analysis Plan	Title Statistical Analysis Plan for: Contour Neurovascular System [™] European PreMarket Unruptured Aneurysm Study (CERUS)			
Confidential & Proprietary				

7 Analysis of Study Endpoints

Primary Safety Endpoint

The primary safety endpoint will be calculated as the proportion of subjects with death of any nonaccidental cause or any major disabling stroke within the first 30 days after treatment or major disabling stroke or death due to neurological cause from day 31 to 6 months after treatment.

Where "Major Disabling Stroke" is defined as an episode of neurological signs or symptoms that persist beyond 24 hours accompanied with evidence of ischemia/infarction on imaging that results in an increase of NIHSS from baseline by ³ 4 points and/or an increase from mRS baseline by >2.

Primary Performance Endpoint

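### A survivor of a disabling intracranial hemorrhage without ischemia or infarction on imaging counts as free of the primary safety event

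*Protocol*

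**What the plan says.** The composite has two windows. Through day 30 it counts any non-accidental death or major disabling stroke; from day 31 to 6 months it counts major disabling stroke or neurological death.

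Major Disabling Stroke is defined four times, each with the same imaging condition:

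- Protocol 10.5.1: "neurological signs or symptoms that persist beyond 24 hours accompanied with evidence of ischemia/infarction on imaging"
- Protocol synopsis (section 2): "accompanied with evidence of ischemia/infarction on imaging"
- SAP summary, Objective and Endpoints: "accompanied with evidence of ischemia/infarction on imaging that results in an increase of NIHSS from baseline by"
- SAP section 7, which specifies the calculation: "an episode of neurological signs or symptoms that persist beyond 24 hours accompanied with evidence of ischemia/infarction on imaging"

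The clinical threshold is a 4-point NIHSS increase (the comparison sign is garbled in the text available to us) and/or an mRS increase of more than 2. The imaging condition applies to both branches. Protocol 10.3 restates the endpoint with the undefined term major stroke.

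Elsewhere, Protocol 6.1 lists "CVA – hemorrhagic" on its own line, apart from ischemic CVA. It also lists aneurysm rupture, subarachnoid hemorrhage (SAH), parenchymatous hematoma and intraventricular hemorrhage, each at under 5%. The pilot study synopsis (Appendix D, 19.3) named among the events to be evaluated "major ipsilateral stroke/subarachnoid hemorrhage (SAH) or death due to neurologic cause within six (6) months after treatment". On testing, Protocol 10.7 states: "No formal hypothesis testing of the study endpoints will be performed".

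**The concern.** In the treatment of an unruptured aneurysm, bleeding is one of the two ways a subject can be left disabled by a stroke. The primary safety endpoint registers the ischemic way and, for survivors, not the hemorrhagic way. Following the plan exactly can therefore give a headline proportion that omits a disabling harm the protocol itself anticipates, while a reader would naturally take that proportion to cover disabling stroke in general. The documents give no reason for restricting the endpoint to ischemia.

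The stake is interpretation. Protocol section 10 says the study is unpowered and that clinical judgement will be applied to the data, so the descriptive safety proportion is a leading item of evidence for the Notified Body and possibly the FDA.

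**Working it through.** **Step 1. Apply the rule.** A stroke counts only if all three hold: symptoms beyond 24 hours, ischemia or infarction on imaging, and the NIHSS or mRS threshold. The only other components are deaths.

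| Subject | Counted? |
|---|---|
| Fatal hemorrhage by day 30 | Yes, as non-accidental death |
| Fatal hemorrhage, day 31 to 6 months | Yes, as neurological death |
| Survivor, disabling bleed, imaging also shows ischemia or infarction | Yes, as stroke |
| Survivor, disabling bleed, no ischemia or infarction on imaging | **No component met** |

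The gap is the last row only.

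**Step 2. Compare with the rest of the protocol.**

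- Protocol 6.1 anticipates hemorrhagic CVA, rupture and SAH.
- The baseline history form in Appendix E offers ischemic stroke, intracranial hemorrhage and subarachnoid hemorrhage as types of stroke, so the sponsor's own form treats hemorrhage as stroke.
- Protocol 6.2 suggests a lower rupture risk than coiling as a possible benefit. The primary safety endpoint cannot register a non-fatal disabling rupture unless imaging also shows ischemia or infarction.
- Protocol section 4 says that roughly 30% of patients with SAH from rupture die and roughly 30% of survivors have significant deficits. That makes disabled survivors about 0.7 × 0.3 = 21% of cases. The figure concerns ruptured aneurysms generally, and some of these survivors may have infarction on imaging or fall short of the thresholds. It shows only that disabled survivors are not negligible beside deaths.

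**Step 3. Where the event would appear.** SAP section 7 summarizes serious neurological adverse events by subject and by event, but with no NIHSS or mRS threshold. SAP section 8 adds follow-up summaries and listings. None of these gives the proportion with death or disabling stroke of either type.

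**Step 4. Size.** The plan states no event rate, performance goal or margin, so there is no figure of its own to reproduce. The inputs are 30 subjects with primary follow-up data and at most 35 enrolled. The exact (Clopper-Pearson) 95% interval for zero events has upper limit 1 − 0.025^(1/n); for n = 30 this is 0.1157. For one event the limits are the corresponding beta quantiles.

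| n | Event not counted | Event counted | Shift |
|---|---|---|---|
| 30 | 0/30 = 0% (0 to 11.6%) | 1/30 = 3.3% (0.1 to 17.2%) | 3.3 points |
| 35 | 0/35 = 0% (0 to 10.0%) | 1/35 = 2.9% (0.1 to 14.9%) | 2.9 points |

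**Step 5. How likely is at least one?** This cannot be derived. The protocol gives only under 5% for hemorrhagic CVA of any severity, and Protocol 7.9 says that "the likelihood of post-placement neurologic changes is very low". For an *assumed* true risk p of an uncounted event, the chance of at least one is 1 − (1 − p)^n:

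| Assumed p | 0.1% | 0.5% | 1% | 2% | 3% |
|---|---|---|---|---|---|
| n = 30 | 3% | 14% | 26% | 45% | 60% |
| n = 35 | 3% | 16% | 30% | 51% | 66% |

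These are illustrations, not estimates.

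**The case against.** The strongest reply is that nothing is lost. A bleed causing permanent impairment is a serious adverse event under Protocol 8.1, so it enters a named secondary safety endpoint. The Clinical Events Committee (CEC) reviews it, and it appears in listings. With about 30 subjects a reader could combine the figures by hand. No hypothesis is tested, and the definition is printed beside the endpoint.

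This stands as a limit on severity: the event is visible and no decision rule changes. It does not supply the missing rate, because the secondary summary applies no disability threshold.

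The supporting comparisons can also be challenged. A composite need not contain every risk in 6.1, and the pilot list is an open list of adverse events, not a thresholded composite. Both points are fair; the conclusion rests on the definition itself, not on these comparisons. The plan also calls for no confidence intervals, so those above only describe precision. The higher probabilities in Step 5 depend wholly on the assumed risk and carry no weight for severity.

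Finally, the schedule contains no routine post-procedure brain CT or MRI, so one may ask what imaging would establish hemorrhage. The current definition already relies on unscheduled diagnostic imaging to show ischemia, and the same imaging would serve.

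**Conclusion.** The concern holds. All four definitions require ischemia or infarction on imaging, so a survivor of a disabling bleed without it is counted as free of the primary safety event. Each such subject lowers the reported rate by 3.3 points at n = 30 or 2.9 points at n = 35. Fatal bleeds that meet the death criteria, and bleeds with ischemia or infarction on imaging, are unaffected. No error rate, power or success criterion is involved. The conclusion follows from the text alone; only the likelihood of the event needs an assumption. This is a design choice that should be fixed, and the improvement is cheap.

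**What to change.** **Preferred.** In the Protocol synopsis, Protocol 10.5.1, the SAP summary and SAP section 7, widen the imaging condition to ischemia/infarction *or intracranial hemorrhage (including SAH or aneurysm rupture)*, keeping the stated NIHSS and mRS thresholds. Have the CEC classify each counted stroke as ischemic or hemorrhagic, and report both components beside the composite. If data have already accrued, report the results under the current and the amended definitions side by side.

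**Minimum, if ischemic-only is intended.** Say so, justify it, and add one SAP table giving the proportion with death or disabling stroke of either type under the same thresholds and time windows.

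**Separately.** Replace the undefined major stroke in Protocol 10.3 with the defined term. This is a consistency correction and adds nothing to the severity of the main point.

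**Cost.** The preferred change amends an endpoint, so under Protocol 12.2.4 it falls outside the changes for which simple notification can suffice. Stroke typing is a small task not named among the CEC's listed classifications (Protocol 9.1). No new assessments are needed: NIHSS is already due within 24 hours of a diagnosed stroke and mRS at every scheduled visit. The reported rate may be less favorable. The minimum option is cheaper and leaves the primary endpoint unchanged, but the headline proportion stays ischemic-only.
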